## 5.2 Dose Interruptions/Withholding

Study treatment, including APR-548 and azacitidine, may be withheld from a subject in the event of intercurrent illness, TEAE, administrative reasons, or other reasons. If the subject's condition subsequently improves, or the situation that resulted in withholding study drug resolves, the investigator may resume dosing as soon as possible, unless the reason for dose interruption falls into one of the categories noted below.

Dosing with APR-548 may be permanently discontinued in any subject who develops any retinopathy or optic nerve disorder (of  $\geq$ Grade 2), regardless of perceived attribution to study drug, and if a clinical retina specialist or ophthalmologist determines a retinal or optic nerve finding is substantially and clinically significantly changed from the subject's baseline test, and that continued participation in the trial would increase the risk for such a finding to worsen (see [Table 7](#) for details).

Dose management guidelines in [Table 2](#) or [Table 3](#) should be followed for each occurrence of a  $\geq$ Grade 3 hematologic or non-hematologic toxicity where relationship to APR-548 and/or azacitidine cannot be excluded (e.g., due to underlying disease).

Dose management guidelines in [Table 4](#), [Table 5](#) and [Table 6](#), respectively, should be followed for each occurrence of infections, nausea/vomiting/diarrhea, and neutropenia with and without fever.

Dose management guidelines in [Table 8](#), [Table 9](#) and [Table 10](#), respectively, should be followed for each occurrence of CNS-associated TEAEs, renal TEAEs (serum creatinine elevations or acute kidney injury), or hepatic TEAEs (elevations in bilirubin, ALT and/or AST).

Subjects experiencing  $\geq$ 2 occurrences of the same TEAE where attribution to APR-548 and/or azacitidine cannot be excluded (e.g., due to underlying disease), the investigator should consult with the study Medical Monitor before study treatments are resumed or discontinued.

Treatment may be discontinued if a TEAE has not improved ( $\leq$ Grade 1 or baseline level) or resolved after  $\leq$ 4 weeks. Consult with the study Medical Monitor to discuss the subject's condition before permanently discontinuing study treatment.

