### 5.1.3 Dose-Limiting Toxicity

All treatment-emergent adverse events (TEAEs) are relevant to the determination of DLTs unless they are clearly and solely due to the disease under study. During the 28-day safety run-in period for APR-548 monotherapy and during the 28-day safety run-in period for APR-548 in combination with azacitidine, a DLT is defined as any of the following TEAEs defined by the National Cancer Institute Common Terminology Criteria for Adverse Events (NCI-CTCAE) version 5.0, as follows:

- Non-hematological NCI-CTCAE  $\geq$ Grade 3 AE, including ocular AEs that are different from retinopathy or optic nerve disorder classifications.
- Prolonged myelosuppression with the persistence of  $\geq$ Grade 4 neutropenia or thrombocytopenia in the absence of disease lasting 14 days from the initial

administration of APR-548 (only during the safety run-in period for APR-548 monotherapy).

- Grade 3 nausea/vomiting/diarrhea/fatigue/CNS AE. Grade 3 nausea/vomiting/diarrhea may be excluded if parenteral nutrition, tube feeding, or prolonged hospitalization is not required.
- New or worsening retinopathy or optic nerve disorder AE of any grade.
- Grade 3 metabolic/electrolyte abnormalities that do not resolve to  $\leq$ Grade 1 or baseline within 72 hours.
- Grade  $\geq$ 4 neutropenia lasting past day 28 in the absence of disease.
- Any AE, regardless of the NCI-CTCAE Grade, resulting in discontinuation, dose reduction or treatment with less than 75% of planned doses of APR-548, unless clearly and solely related to disease under study.

Investigator should contact the Medical Monitor to discuss any findings suggestive of ocular-associated AEs. Any  $\geq$ Grade 2 ocular-associated AEs are considered AEs of special interest and should be reported as SAEs. Subjects with signs and/or symptoms of vision changes should be seen immediately by ophthalmologist/retinal specialist. APR-548 may be permanently discontinued, following a discussion with the Medical Monitor, if:

- Any retinopathy or optic nerve disorder develops, regardless of perceived attribution to study drug, and
- A clinical retina specialist or ophthalmologist determines a retinal or optic nerve finding is substantially changed from the subject's baseline test.

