**Table 2. Dose management guidelines for new onset hematologic toxicities**

Toxicity	Occurrence	APR-548	Azacitidine
Grade 3 or 4 hematologic toxicity *	1 st occurrence 
 
Hold all study treatments until blood count(s) return to baseline or Grade <math>\leq</math>1. Treat promptly.
 
	
 
Consider reducing APR-548 by one dose level from starting dose for all future cycles of treatment if toxicity does not resolve to Grade <math>\leq</math>1 within 7 days from onset date despite maximal medical intervention(s).
 
If unable to reduce APR-548 dose, discuss with study Medical Monitor before resuming or discontinuing treatment.
 
	
 
Follow dose modification guidelines per USPI.
 

	2 nd or later occurrence 
 
Hold all study treatments until blood count(s) return to baseline or Grade <math>\leq</math>1. Treat promptly.
 
	
 
Consult with study Medical Monitor before resuming or discontinuing study treatments.
 
	

\* Grade 3 and Grade 4 neutropenia with fever or Grade 4 neutropenia without fever should follow the guidelines provided in [Table 6](#).

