**Table 3. Dose management guidelines for non-hematologic toxicities**

Toxicity	Occurrence	APR-548	Azacitidine
Grade 3 or 4 non-hematologic toxicity *	1 st occurrence 
 
Hold all study treatments until toxicity returns to baseline or Grade <math>\leq</math>1. Treat promptly.
 
	
 
Consider reducing APR-548 by one dose level from starting dose for all future cycles of treatment if toxicity does not resolve to Grade <math>\leq</math>1 within 7 days from onset date despite maximal medical intervention(s).
 
If unable to reduce APR-548 dose, discuss with study Medical Monitor before resuming treatment.
 
	
 
Follow dose modification guidelines per USPI.
 

	2 nd or later occurrence 
 
Hold all study treatments until toxicity returns to
 
	
 
Consult with study Medical Monitor before resuming study treatments.
 
	

	baseline or Grade $\leq$ 1. Treat promptly.	
--	--	--

\*For infections and infestation, nausea/vomiting/diarrhea,  $\geq$  Grade 3 neutropenia, CNS-associated TEAEs, Renal TEAEs, or hepatic TEAEs, refer to [Table 4](#), [Table 5](#), [Table 6](#), [Table 8](#), [Table 9](#) and [Table 10](#), respectively for dose management guidelines.

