**Table 7. Management of ocular-associated adverse events**

Parameter	Worst toxicity	Occurrence	Dose Modifications for APR-548
Retinopathy and optic nerve disorders	Grade 1	1 st occurrence	Interrupt treatment with APR-548. Monitor and treat patient promptly as clinically indicated. Consult with study medical monitor before resuming dosing of APR-548 at same dose level once event has stabilized or resolved to baseline.
		2 nd occurrence	Interrupt treatment with APR-548. Monitor and treat patient promptly as clinically indicated. Consult with study medical monitor to determine if patient should resume at same dose level or if APR-548 should be reduced by 1 dose level.
		3 rd occurrence	Interrupt treatment with APR-548. Monitor and treat patient promptly as clinically indicated. Consult with study medical monitor to determine if APR-548 treatment should be reduced by one dose level or permanently discontinued.
	Grade 2	1 st occurrence	Interrupt treatment with APR-548. Monitor and treat patient promptly as clinically indicated. Notify medical monitor and report as SAE (AESI). Once resolved to baseline parameters, then reduce dose of APR-548 by one level. If unable to reduce dose of APR-548, discuss with study medical monitor before resuming or discontinuing treatment with APR-548.
		2 nd occurrence	Permanently discontinue treatment with APR-548. Monitor and treat patient promptly as clinically indicated. Notify medical monitor and report as SAE (AESI).
	≥Grade 3	N/A	Permanently discontinue subject from APR-548.
	Other	Grade 1	Interrupt treatment with APR-548 for new finding or worsening from baseline. Monitor and treat patient promptly as clinically indicated. May resume at current dose level once stabilized or resolved to baseline. Consult with study medical monitor before resuming or reducing dose of APR-548 for a second or greater occurrence of same event.
	Grade 2	1 st occurrence	Interrupt treatment with APR-548 for new finding or worsening from baseline. Monitor and treat patient promptly as clinically indicated. Notify Medical Monitor and report as SAE (AESI).

		Once resolved to baseline parameters, then: First occurrence, reduce dose of APR-548 by one level. If unable to reduce dose of APR-548, discuss with study medical monitor before resuming or discontinuing treatment with APR-548.

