	2 nd occurrence	Permanently discontinue treatment with APR-548. Monitor and treat patient promptly as clinically indicated. Notify Medical Monitor and report as SAE (AESI).
≥Grade 3	N/A	Permanently discontinue subject from APR-548.

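### A Grade 3 or higher ocular event falls under two APR-548 dosing instructions, and the visible text does not say that Table 7 overrides Table 3

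*Combined protocol and SAP*

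**What the plan says.** **General route (5.2 and Table 3).** Section 5.2 directs sites to Table 2 or Table 3 for each event at or above "Grade 3 hematologic or non-hematologic toxicity where relationship to APR-548 and/or azacitidine cannot be excluded". Table 3 covers Grade 3 or 4 non-hematologic toxicity. At a first occurrence, all study treatments are held until baseline or Grade 1 or lower. A one-level APR-548 reduction is considered if recovery takes more than 7 days, and the row ends: "If unable to reduce APR-548 dose, discuss with study Medical Monitor before resuming treatment". At a second or later occurrence, treatments are held again and the site is told: "Consult with study Medical Monitor before resuming study treatments". The footnote lists the exceptions, ending with "CNS-associated TEAEs, Renal TEAEs, or hepatic TEAEs, refer to" and the numbers of Tables 4, 5, 6, 8, 9 and 10.

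**Ocular route (Table 7).** Table 7 has two groups: retinopathy and optic nerve disorders, and Other. In both, the Grade 3 or higher row reads "Permanently discontinue subject from APR-548". In both, the second Grade 2 row reads "Permanently discontinue treatment with APR-548. Monitor and treat patient promptly as clinically indicated. Notify Medical Monitor and report as SAE (AESI").

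**Prose on stopping.** Section 5.1.3 and the synopsis say that APR-548 *may* be permanently discontinued, after discussion with the Medical Monitor, if retinopathy or optic nerve disorder develops and a specialist finds a substantial change from baseline. Section 5.2 also says *may*, for such disorders of Grade 2 or higher. It adds that the change must be clinically significant and that continuing would raise the risk of worsening. That sentence ends with a reference to Table 7 for details.

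**The concern.** An ocular event is a non-hematologic event, so on a plain reading a Grade 3 or higher ocular event that may be drug-related meets the entry condition of Table 3 as well as that of Table 7. The two tables lead to different places for APR-548: one to a hold with a path back to dosing, the other to a permanent stop. A site that follows 5.2 and Table 3 as written could re-dose a subject whom Table 7 bars.

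This matters because the trial is first-in-human and treats ocular events of Grade 2 or higher as adverse events of special interest, reportable as serious. The stopping criterion in 8.4 for Grade 3 or higher ocular events suspends enrollment pending review by the Data Review Team. It does not say what happens to the affected subject's own dosing.

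**Working it through.** No arithmetic figure is at issue. The check sets the instructions side by side and asks whether any visible text ranks them.

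**1. Do ocular events enter Table 3?** Yes. The 5.2 sentence has no ocular exception. The first bullet of 5.1.3 places some ocular events under the non-hematological heading, at or above "Grade 3 AE, including ocular AEs that are different from retinopathy or optic nerve disorder classifications".

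**2. Does the Table 3 footnote take them out?** No. It names six groups: infections, nausea/vomiting/diarrhea, neutropenia, CNS, renal and hepatic events. These go to Tables 4, 5, 6, 8, 9 and 10. Table 7 is skipped.

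**3. Does the routing text in 5.2 take them out?** Not for all ocular events. The sentences that tell sites which tables to follow cover Tables 2 and 3, then 4 to 6, then 8 to 10. That is 2 + 3 + 3 = 8 of the 9 dose-management tables numbered 2 to 10. Section 5.2 does mention Table 7, once, in the paragraph on retinopathy and optic nerve disorders of Grade 2 or higher. Apart from the list of tables, that is the only pointer to Table 7 in the visible text.

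**4. Which Table 7 rows are affected?** Retinopathy and optic nerve disorders have 6 rows (Grade 1 first, second and third; Grade 2 first and second; Grade 3 or higher). Other has 4 (Grade 1; Grade 2 first and second; Grade 3 or higher). Total: 6 + 4 = 10. Four rows order a permanent stop:

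| Table 7 row | Competing Table 3 instruction | Pointer to Table 7 | Ocular-specific prose on stopping |
|---|---|---|---|
| Retinopathy/optic nerve, second Grade 2 | No, below Grade 3 | Yes, in 5.2 | *May*, with conditions |
| Retinopathy/optic nerve, Grade 3 or higher | Yes | Yes, in 5.2 | *May*, with conditions |
| Other, second Grade 2 | No, below Grade 3 | None | None |
| Other, Grade 3 or higher | Yes | None | None |

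The columns classify the same four rows in different ways, so their counts must not be added. Two rows of ten have a competing Table 3 instruction. One row of ten, Other at Grade 3 or higher, has both a competing instruction and no pointer.

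**5. How far apart are the instructions?** Table 7's stop carries no attribution condition and no specialist-finding condition. Table 3 requires a Medical Monitor discussion at a first occurrence only if the dose cannot be reduced. On Table 3 alone, a first Grade 3 event that recovers within 7 days leads back to dosing at the same level. Table 3 also holds azacitidine until recovery, whereas Table 7 speaks only of APR-548.

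**The case against.** The best reply is that the specific table governs the general one. Table 7 is devoted to ocular events, sits within 5.2 and has its own Other group. If Table 3 prevailed, both of Table 7's Grade 3 or higher rows would be pointless whenever a relationship cannot be excluded. This makes the intent fairly clear, but it does not settle the text. The Table 3 footnote writes its exceptions out and leaves this one off, and the only pointer to Table 7 is attached to a conditional *may* about one of the two ocular groups.

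A reader might infer that the prose contradicts Table 7 or makes its stops optional. The documents do not support that. The *may* sentences reach events for which Table 7 orders no stop, such as a first Grade 2 event, and they can be read as allowing an earlier stop. Stopping under Table 7 breaches none of them. What remains is that the prose is weaker than the table in the rows where the table is mandatory.

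A reader might also infer that Table 3 orders re-dosing, because it never mentions discontinuation, while Table 2 has "Consult with study Medical Monitor before resuming or discontinuing study treatments". That contrast carries little weight. Section 5.2 allows discontinuation for a toxicity that does not improve, and 4.10.1 requires it for unacceptable risk. Table 3 opens a path back to dosing but does not compel it. Nor does the 5.2 sentence on repeat events conflict with Table 7: it concerns recurrences of the same event with attribution not excluded, and consulting before resuming or discontinuing is compatible with a stop.

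The safeguards are substantial. Sites are told to contact the Medical Monitor about ocular findings, and subjects with vision changes are seen immediately by a specialist (5.1.3). Serious events are reported within 24 hours (7.1.2.6), and the Medical Monitor reviews all of them (7.1.2.7). Scheduled eye evaluations precede the next scheduled dose (Table 16, footnote a). APR-548 is planned for Days 1 to 4 of each 28-day cycle. Unnoticed re-dosing is therefore unlikely, although the Medical Monitor would be reading the same two tables.

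**Conclusion.** The point holds, as a minor correction to a patient-safety rule. In the visible text, a Grade 3 or higher ocular event whose relationship to study treatment cannot be excluded has two APR-548 instructions and no statement of which prevails. The gap is sharpest for Other ocular events at that grade. For retinopathy and optic nerve disorders the pointer exists, but the prose is conditional where Table 7 is not, at Grade 3 or higher and at a second Grade 2 event.

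A reader might infer an effect on dose-limiting toxicity counts or on escalation. The documents do not support this. In the evaluation windows, 5.1.3 already counts Grade 3 or higher non-hematological events, including other ocular events, and any new or worsening retinopathy or optic nerve disorder, whichever dosing table a site follows. No analysis or escalation decision is shown to change.

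Two assumptions apply. Table 7 is taken to be the intended rule. The finding that no text ranks the tables is limited to what can be read: Potential Risks (2.8.1) is almost wholly blacked out, as is part of 4.1.

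**What to change.** - **Table 3 footnote and the routing sentences in 5.2:** add ocular-associated events, with Table 7 governing APR-548, and state that this covers both retinopathy/optic nerve disorders and Other.
- **Azacitidine:** state that Table 3's hold on azacitidine until recovery still applies to ocular events of Grade 3 or higher. Without this, moving ocular events wholly to Table 7 would remove that hold.
- **5.1.3, the synopsis and 5.2:** say that APR-548 must be permanently discontinued where Table 7 orders it (Grade 3 or higher, or a second Grade 2 event), and keep *may* for other ocular events.

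The cost is a few words in the Table 3 footnote, 5.2, 5.1.3 and the synopsis. No visit or procedure is added and no Table 7 rule changes.

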**Table 2. Dose management guidelines for new onset hematologic toxicities**

Toxicity	Occurrence	APR-548	Azacitidine
Grade 3 or 4 hematologic toxicity *	1 st occurrence 
 
Hold all study treatments until blood count(s) return to baseline or Grade <math>\leq</math>1. Treat promptly.
 
	
 
Consider reducing APR-548 by one dose level from starting dose for all future cycles of treatment if toxicity does not resolve to Grade <math>\leq</math>1 within 7 days from onset date despite maximal medical intervention(s).
 
If unable to reduce APR-548 dose, discuss with study Medical Monitor before resuming or discontinuing treatment.
 
	
 
Follow dose modification guidelines per USPI.
 

	2 nd or later occurrence 
 
Hold all study treatments until blood count(s) return to baseline or Grade <math>\leq</math>1. Treat promptly.
 
	
 
Consult with study Medical Monitor before resuming or discontinuing study treatments.
 
	

\* Grade 3 and Grade 4 neutropenia with fever or Grade 4 neutropenia without fever should follow the guidelines provided in [Table 6](#).

**Table 3. Dose management guidelines for non-hematologic toxicities**

Toxicity	Occurrence	APR-548	Azacitidine
Grade 3 or 4 non-hematologic toxicity *	1 st occurrence 
 
Hold all study treatments until toxicity returns to baseline or Grade <math>\leq</math>1. Treat promptly.
 
	
 
Consider reducing APR-548 by one dose level from starting dose for all future cycles of treatment if toxicity does not resolve to Grade <math>\leq</math>1 within 7 days from onset date despite maximal medical intervention(s).
 
If unable to reduce APR-548 dose, discuss with study Medical Monitor before resuming treatment.
 
	
 
Follow dose modification guidelines per USPI.
 

	2 nd or later occurrence 
 
Hold all study treatments until toxicity returns to
 
	
 
Consult with study Medical Monitor before resuming study treatments.
 
	

	baseline or Grade $\leq$ 1. Treat promptly.	
--	--	--

\*For infections and infestation, nausea/vomiting/diarrhea,  $\geq$  Grade 3 neutropenia, CNS-associated TEAEs, Renal TEAEs, or hepatic TEAEs, refer to [Table 4](#), [Table 5](#), [Table 6](#), [Table 8](#), [Table 9](#) and [Table 10](#), respectively for dose management guidelines.

**Table 4. APR-548 and azacitidine dose management guidelines for infection and/or infestation adverse events**

Toxicity Grade	Occurrence	APR-548	Azacitidine
Grade 3 or 4	1 st occurrence	
 
Interrupt dosing and monitor subject; treat promptly.
 
Resume at current dose level if toxicity returns to baseline or Grade <math>\leq</math> 1 in less than 7 days from onset date.
 
Reduce APR-548 by one dose level from starting dose for all future cycles of treatment if toxicity does not resolve to Grade <math>\leq</math> 1 within 7 days of onset date.
 
If unable to reduce APR-548 dose, discuss with study Medical Monitor before resuming or discontinuing treatment.
 
Initiate or reassess infection prophylaxis measures. Refer to Section 5.3.3 for supportive management guidelines specific to infections or infestations.
 
	Follow dose modification guidelines per USPI  .
	2 nd occurrence	
 
Hold all study treatments and monitor subject; treat promptly.
 
Assess current infection prophylaxis measures being administered and adjust treatment plan as clinically indicated. Refer to Section 5.3.3 for supportive management guidelines specific to infections or infestations.
 
While APR-548 and azacitidine are interrupted, consult with study Medical Monitor before resuming or discontinuing study treatments.
 
	

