	
(average maximum concentration [<math>C_{max}</math>] and area under the curve [AUC] 8 <math>\mu</math>M and 16 <math>\mu</math>M·h, respectively) is reached, or the minimum biologically effective dose (mBED) is achieved (the dose at which no further incremental effect on markers of apoptosis and/or proliferation is observed, in the monotherapy safety run-in only). The Data Review Team (DRT), consisting of the Medical Monitor, Site Principal Investigators, retina specialist and other clinical research personnel that the Sponsor deems appropriate, will review the available PK, PD and safety data for each 3-6 subject cohort in both the safety run-in for the monotherapy and the combination portions, and increases in dose will be guided by the observed safety, PK and PD data, until the recommended phase 2 dose (RP2D) is determined. The RP2D of APR-548 will be defined as the lowest of:
 

1. The mBED in the monotherapy safety run-in,

2. The dose that achieves the pre-defined level of maximum exposure in the monotherapy or combination therapy safety run-ins, or

3. The dose at which there are <2 DLTs in 3-6 subjects in a cohort, in the monotherapy or combination therapy safety run-ins.

 
Up to 10 subjects may be enrolled at the RP2D per decision of the DRT to gain additional confidence in the RP2D.
 
Subjects in Cohort 1 will receive a starting APR-548 dose of 50 mg/day (Dose level 1). If there is a DLT in <math>\leq 1/3</math> subjects in Cohort 1, Cohort 1 will be expanded to enroll 3 more subjects. If <math>\geq 2</math> subjects out of the total 3-6 subjects have a DLT, dose escalation will not occur. If <math>\leq 1</math> DLT occurs in the 6 subjects treated at that dose level, the subsequent subject group (Cohort 2) will be enrolled upon DRT review of data as described above, at the APR-548 dose of 150 mg/day (Dose level 2). If <math>\geq 2</math> of 6 subjects at a dose level have a DLT, or if the pre-defined maximum exposure of APR-548 in plasma is reached or the minimum biological effective dose is achieved (in monotherapy safety run-in only), then dose escalation ceases. This study will evaluate up to 6 dose levels. Any subsequent dose escalation will not exceed 100% and will follow the same cohort escalation plan as outlined above and in Figure 1.

--	---

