Subjects in Cohort 1 will receive a starting dose of 50 mg/day (Dose level 1). If there is a DLT in  $\leq 1/3$  subjects in Cohort 1, Cohort 1 will be expanded to enroll 3 more subjects. If  $\geq 2$  subjects out of the total 3-6 subjects have a DLT, dose escalation will not occur. If  $\leq 1$  DLT occurs in the 6 subjects treated at that dose level, the subsequent subject group (Cohort 2) will be enrolled upon DRT review of data as described above, at the APR-548 dose of 150 mg/day (Dose level 2). If  $\geq 2$  of 6 subjects at a dose level have a DLT, or if the pre-defined maximum exposure of APR-548 in plasma is reached or the mBED is achieved (in monotherapy safety run-in only), then dose escalation ceases. This study will evaluate up to 6 dose levels. Any subsequent dose escalation will not exceed 100% and will follow the same principle as described above. The table below shows the planned dose levels based on the expected APR-548 human PK and under the assumption that the doses are well tolerated. Once the RP2D is established, if only 3 subjects were treated at the RP2D, an additional 3 subjects will be included in the cohort and if  $\leq 1$  DLT occurs in the 6 subjects treated at that dose level, the RP2D will be defined.

The [REDACTED]

[REDACTED]

[REDACTED]

[REDACTED]

The DRT will also review any other emergent toxicities that are not explicitly defined by the DLT criteria to determine if any warrant a DLT designation.

If the dose escalation of the 28-day safety run-in proceeds more rapidly than the combination portion such that the dose of APR-548 undergoing evaluation in the 28-day safety run-in exceeds that being assessed in the combination portion, the subject will receive the dose of APR-548 currently being assessed for safety in the combination portion. If a subject in the 28-day safety run-in period has a dose reduction of APR-548 due to AE, the subject will proceed with Cycle 1 of the combination portion with the reduced dose of APR-548 in combination with standard dose azacitidine.

Following discussions with the DRT, the schedule of APR-548 may be modified, including multiple daily and weekly doses, based on available PK, PD, and safety data.

Subjects in the 28-day safety run-in period and in Cycle 1 of the combination portion who miss  $\geq 25\%$  of APR-548 doses for a nonmedical reason (e.g., subject's preference) or noncompliance will be replaced.

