### 5.1.1 APR-548

The APR-548 starting dose is 50 mg/day administered p.o during Days 1–4 for the 28-day safety run-in and in the 28-day cycles in the combination portion.

APR-548 is distributed to sites as a powder in bottle for oral solution. APR-548 should be reconstituted with cold sterile water as follows:

- 150 mg bottle once reconstituted with 30 mL of cold sterile water will be 5 mg/mL.
- 150 mg bottle once reconstituted with 10 mL of cold sterile water will be 15 mg/mL.
- 300 mg bottle once reconstituted with 10 mL of cold sterile water will be 30 mg/mL.

The prepared solution should be taken with an additional 200 mL of water at least 2 hours after and 1 hour before any food intake.

Detailed instructions on vial concentration, preparation and dispensing can be found in the Pharmacy Binder.

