**Table 5. APR-548 dose management guidelines for nausea, vomiting, and/or diarrhea adverse events**

Worst toxicity grade	Dose modification guidelines for APR-548 *
Grade 1	
 
Maintain dose level of APR-548 and monitor subject; provide supportive care measures as clinically indicated.
 

Grade 2	
 
Interrupt APR-548 dosing and monitor subject; treat promptly.
 
Resume at current dose level if toxicity resolves to Grade <math>\leq</math> 1 or baseline, with or without use of supportive care measures, within 72 hours of onset.
 
If toxicity does not resolve to Grade <math>\leq</math> 1 within 72 hours despite maximal medical intervention(s), then reduce APR-548 by 1 dose level once the toxicity resolves to
 

		
Grade ≤1 or baseline.
 
 
• If unable to reduce APR-548 dose, discuss with study Medical Monitor before resuming or discontinuing treatment.
 
• For subsequent doses of APR-548, pre-medication with prophylactic supportive therapy should be given if clinically indicated.
 

Grade 3	1 st occurrence	
 
• Interrupt APR-548 dosing and monitor subject; treat promptly.
 
• Resume at current dose level if toxicity resolves to Grade ≤1 or baseline, with supportive care measures, within 72 hours of onset.
 
• If toxicity does not resolve to Grade ≤1 within 72 hours despite maximal medical intervention(s), then reduce APR-548 by 1 dose level once the toxicity resolves to Grade ≤1 or baseline.
 
• If unable to reduce APR-548 dose, discuss with study Medical Monitor before resuming or discontinuing treatment.
 
• For subsequent doses of APR-548, pre-medication with prophylactic supportive therapy should be given.
 

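### Tables 2 to 4 tie the APR-548 reduction to an undefined starting dose, so a subject already cut from 300 to 150 mg may get no further reduction after an unresolved severe infection

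*Combined protocol and SAP*

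**What the plan says.** Section 5.2 gives the rules for changing the dose after toxicity. For a first Grade 3-4 infection, Table 4 has one instruction if the event resolves in under 7 days and another if it does not. The first is "Resume at current dose level if toxicity returns to baseline" or Grade 1 or lower. The second is "Reduce APR-548 by one dose level from starting dose for all future cycles of treatment". A further bullet covers the case where no cut is possible: "If unable to reduce APR-548 dose, discuss with study Medical Monitor before resuming or discontinuing treatment".

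Tables 2 and 3 cover other first Grade 3-4 hematologic and non-hematologic events unresolved at 7 days. They share the anchor but leave the step optional: "Consider reducing APR-548 by one dose level from starting dose for all future cycles of treatment".

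Tables 5 and 6 have no such anchor. Table 5, for nausea, vomiting or diarrhea of Grade 2 or a first Grade 3 event unresolved at 72 hours, says "then reduce APR-548 by 1 dose level once the toxicity resolves to" Grade 1 or lower, or baseline. Table 6, for neutropenia unresolved at 7 days, is worded in the same way.

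Section 5.2 does not define the starting dose. Section 5.1.1 uses the term for the trial's entry dose: "The APR-548 starting dose is 50 mg/day administered p.o". The Synopsis and Section 4.1 use it in the same sense.

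**The concern.** A dose cut after severe toxicity should be measured from the dose the subject was taking when the event began. Table 4 measures it from a different point and does not say what that point is. Because the same table cell also speaks of a current dose level, the two terms cannot be assumed to mean the same thing.

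At stake is the dose that a subject resumes in a first-in-human trial after a Grade 3-4 infection that had not settled by day 7. Sites that read the term differently would give different doses after the same event.

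**Working it through.** The plan gives no figure of its own for this rule, so the check applies the rule to the planned dose levels.

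**Inputs.** The preliminary levels are 50, 150 and 300 mg/day (Synopsis, Figure 1). The cut is (dose at onset − target) / dose at onset.

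**Meaning A: the trial's entry dose, 50 mg/day.** No level lies below 50 mg. Every case falls to the Medical Monitor bullet, so the reduction that Table 4 directs can never be made.

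**Meaning B: the subject's own initial dose.** The target is one level below the initial dose. **Meaning C**, for comparison, is one level below the dose at onset, which is how an unanchored one-level cut is naturally read.

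| Initial dose, mg | Dose at onset, mg | Target under B | Target under C |
|---|---|---|---|
| 150 | 150 | 50 | 50 |
| 300 | 300 | 150 | 150 |
| 300 | 150 | 150: (150 − 150)/150 = 0% cut | 50: (150 − 50)/150 = 67% cut |
| 300 | 50 | 150, above the dose at onset | none lower: Medical Monitor |
| 150 | 50 | 50: (50 − 50)/50 = 0% cut | none lower: Medical Monitor |
| 150 | 300 (escalated) | 50: (300 − 50)/300 = 83% cut | 150: (300 − 150)/300 = 50% cut |

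1. While the dose is unchanged, B and C agree.
2. After an earlier cut, B never reduces. If the initial dose is level i and the dose at onset is level j below i, the target is level i − 1, which is at or above j.
3. In two of the three already-reduced histories the subject is at 50 mg. No lower level exists, so the Medical Monitor step applies.
4. In the third, 300 cut to 150 mg, a 50 mg level is available. The Medical Monitor step is therefore not clearly triggered.
5. The escalated case (escalation within a subject is allowed by Section 4.1) errs toward caution.

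**Can the third history arise?** Yes. Table 5 requires a one-level cut for unresolved Grade 2 nausea, vomiting or diarrhea. Table 6 requires one for unresolved neutropenia, and Tables 7 to 9 include cuts for ocular, CNS and renal events. Under Section 4.1 a dose reduced in the monotherapy run-in carries into Cycle 1. A first Grade 3-4 infection can follow any of these.

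**Do the other consultation rules catch it?** The repeat-event consultation in Section 5.2 applies to the same adverse event occurring again. The mandatory consultation in Table 4 begins with the second infection. Neither covers a first infection after a cut for something else.

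**The case against.** The strongest reply is that the harm depends on meaning B, which the text does not establish. The documented use of the term is 50 mg/day, and on that use every case reaches the Medical Monitor, which is clumsy but safe. The instruction is also to reduce: leaving 150 mg at 150 mg is not a reduction, so a site might conclude that it is unable to reduce and call the Medical Monitor. This stands as far as it goes. The text is ambiguous, and it does not plainly order a return to the same dose. A site could even take the term to mean the dose at onset, in which case the fix only states what was intended.

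A reader might infer two stronger points that the documents do not support:

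- **That the rule fails unguarded after every earlier cut, and can raise a dose from 50 to 150 mg.** Where the subject is already at 50 mg, the Medical Monitor step applies. On these levels only the 300-to-150 history is left.
- **That all of Tables 5 to 10 would have lowered the dose.** For severe events several do something else. Table 5 sends Grade 4 to the Medical Monitor, Table 7 stops APR-548 at Grade 3 or above, Table 8 consults if a Grade 3 event does not resolve, and Table 9 leans toward stopping for unresolved Grade 3 creatinine elevation. The fair comparators are Table 6 and Table 5 for Grade 2 or a first Grade 3 event.

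Other safeguards also count. In both 28-day run-ins a Grade 3 infection would ordinarily be a DLT (Section 5.1.3) and go to the Data Review Team. Table 6 also applies where neutropenic fever or new Grade 4 neutropenia is present. The Medical Monitor reviews all SAEs (Section 7.1.2.7), and the investigator may stop treatment at any time (Section 4.10.4). These limit the harm. They do not correct the instruction, and the DLT window does not extend to Cycle 2 and later.

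**Conclusion.** The point holds as a low-severity correction to a safety rule. Neither the protocol's other usage nor the initial-dose meaning gives a rule that works throughout: under the first the directed cut never operates, and under the second it gives no reduction once the dose has already been cut.

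The size is one history on the 50/150/300 mg levels: 300 cut to 150 mg, then a first unresolved Grade 3-4 infection, with a 0% cut where a 67% cut would be expected. This assumes the initial-dose meaning, the preliminary levels (the Synopsis says they may change), and that an unanchored one-level cut starts from the dose at onset. The rule is directive only in Table 4. The documents do not say how often the history would occur. Sample size, endpoints and the escalation rule are not affected.

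**What to change.** In Tables 2, 3 and 4, replace the reference to the starting dose so that the reduction is to one dose level below the dose the subject was receiving at onset of the event. Keep the Medical Monitor step for cases where no lower level exists. With this wording a subject at 150 mg after an earlier cut goes to 50 mg, and subjects whose dose has not changed from an initial 150 or 300 mg get the same result as under the initial-dose meaning.

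The cost is a wording amendment in three tables, with no change to visits, data collection or sample size.
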